4.8.1.2 Deaths

The following deaths summaries will be generated on the all-treated population.

- Number (%) of patients who died during the study and reasons for death
- Number (%) of patients who died within 30 days after the last dose of study drug (excluding those who died after taking any subsequent anticancer therapy/procedure) and reasons for death

4.8.1.3 AE for Transplant/CAR-T patients

The following analysis will be performed for patients who have responded to camidanlumab tesirine and undergo HSCT (either autologous or allogeneic) after permanent discontinuation

of camidanlumab tesirine treatment (without any intervening anticancer therapy to treat relapsing disease but mobilization/conditioning treatment for HSCT is allowed) or who have received CAR-T as the immediate subsequent anticancer therapy (mobilization/conditioning treatment for CAR-T is allowed) (i.e., patient in SCT population/CAR-T population) . The data will include the following information reported until 180 days post-HSCT/post-CAR-T regardless of relationship to camidanlumab tesirine.

- Summary of AEs \geq Grade 3 suggestive of hepatic toxicity, veno-occlusive disease/sinusoidal obstruction syndrome, graft-versus-host disease, infectious complications, potentially immune-mediated adverse events, prolonged cytopenia(s), and pulmonary toxicity
- In addition for CAR-T patients, summary of \geq Grade 3 AEs of cytokine-release-syndrome and neurological toxicity
- SAEs by primary SOC, PT and Maximal CTCAE grade
- Number (%) of patients who died after HSCT/CAR-T and reasons for death

4.8.2 Laboratory Data

Laboratory data of hematology, biochemistry, and coagulation up the end of study visit will be reported in SI units.

Descriptive statistics (mean, standard deviation, median, and range) will be calculated for the raw data and for their changes from baseline at each scheduled assessment for hematology, biochemistry, coagulation. All results will be summarized using shift from baseline. Shifts for clinical laboratory results that can be graded according to CTCAE version 4.0 will be summarized by CTCAE grade.

Summaries by visit will include data from scheduled assessments, and all data will be reported according to the nominal visit date for which it was recorded. Unscheduled data will be included in “worst case post-baseline” summaries, which will capture a worst case across all scheduled and unscheduled visits after the first dose of study treatment.

Summary analyses will include data up to the start of subsequent anticancer therapy/procedure.

All laboratory data, including urinalysis, and as applicable, serology, viral detection, and/or additional microbiological studies will be listed. Pregnancy test results will not be listed, but will be included in datasets.

4.8.3 Electrocardiogram

Descriptive statistics (mean, standard deviation, median and range) for ECG data will be calculated for the raw data and for their changes from baseline at each scheduled assessment.

The following abnormal QTc (including QTcF and QTcB) will be reported by a frequency table:

At any post-baseline with absolute value

>450 - <=480 ms

>480 - <=500 ms

> 500 ms

Change from Baseline

>30 – <=60 ms

>60 ms

Summary analyses will include data up to the start of subsequent anticancer therapy/procedure.

All ECG data will be listed, both for quantitative data and for overall impression.

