- 17. Significant medical comorbidities, including uncontrolled hypertension (blood pressure [BP] ≥ 160/100 mmHg repeatedly), unstable angina, congestive heart failure (greater than New York Heart Association class II), electrocardiographic evidence of acute ischemia, coronary angioplasty or myocardial infarction within 3 months prior to screening, severe uncontrolled atrial or ventricular cardiac arrhythmia, poorly controlled diabetes, or severe chronic pulmonary disease.
- 18. Major surgery, radiotherapy, chemotherapy, or other anti-neoplastic therapy, within 14 days prior to start of study drug, except shorter if approved by the Sponsor.
- 19. Use of any other experimental medication within 30 days prior to start of study drug.
- 20. Any live vaccine within 4 weeks prior to start of study drug and planned live vaccine administration after starting study drug.
- 21. Congenital long QT syndrome, or a corrected QTc interval of ≥ 480 ms, at screening (unless secondary to pacemaker or bundle branch block).
- 22. Any other significant medical illness, abnormality, or condition that would, in the Investigator's judgment, make the patient inappropriate for study participation or put the patient at risk.

Estimated Duration of Patient Participation and Study Duration:

The duration of the study participation for each patient is defined as the time from the date of signed written informed consent to the completion of the follow-up period, withdrawal of consent, loss to follow-up, or death, whichever occurs first.

The study will include a Screening Period (of up to 28 days), a Treatment Period (cycles of 3 weeks), and a Follow-up Period (approximately every 12-week visits) for up to 3 years from End of Treatment (EOT).

Patients may continue treatment until disease progression, unacceptable toxicity, or other discontinuation criteria, whichever occurs first.

The overall end of study occurs at the last visit or last scheduled procedure for the last patient, unless the study is terminated earlier by Sponsor.

Efficacy Assessments:

• Disease assessments: Positron emission tomography-computed tomography (PET-CT)

Note: If disease is not PET-avid at baseline, CT or MRI may be used for follow-up disease assessments. The assessment method determined to identify sites of disease at Baseline should be used for all subsequent assessments.

Safety Assessments:

- Physical examination, including neurological examination
- ECOG performance status
- Height and weight

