- 12. History of Stevens-Johnson syndrome or toxic epidermal necrolysis.
- 13. Failure to recover ≤ Grade 1 (Common Terminology Criteria for Adverse Events version 4.0 [CTCAE v4.0]) from acute non-hematologic toxicity (except ≤ Grade 2 neuropathy or alopecia), due to previous therapy, prior to screening.
- 14. HL with central nervous system involvement, including leptomeningeal disease.
- 15. Clinically significant third space fluid accumulation (i.e., ascites requiring drainage or pleural effusion that is either requiring drainage or associated with shortness of breath).
- 16. Breastfeeding or pregnant.
- 17. Significant medical comorbidities, including uncontrolled hypertension (blood pressure [BP] ≥ 160/100 mmHg repeatedly), unstable angina, congestive heart failure (greater than New York Heart Association class II), electrocardiographic evidence of acute ischemia, coronary angioplasty or myocardial infarction within 3 months prior to screening, severe uncontrolled atrial or ventricular cardiac arrhythmia, poorly controlled diabetes, or severe chronic pulmonary disease.
- 18. Major surgery, radiotherapy, chemotherapy, or other anti-neoplastic therapy, within 14 days prior to start of study drug, except shorter if approved by the Sponsor.
- 19. Use of any other experimental medication within 30 days prior to start of study drug.

- 20. Any live vaccine within 4 weeks prior to start of study drug and planned live vaccine administration after starting study drug.
- 21. Congenital long QT syndrome, or a corrected QTc interval of \geq 480 ms, at screening (unless secondary to pacemaker or bundle branch block).
- 22. Any other significant medical illness, abnormality, or condition that would, in the Investigator's judgment, make the patient inappropriate for study participation or put the patient at risk.

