7.4.7 ECG

Three consecutive (also called triplicate) 12-lead ECGs will be performed at defined timepoints throughout the study as per SoE (Table 1). Refer to Table 3 for the detailed schedule of ECGs. The ECGs will be performed after the patient is resting for at least 5 minutes.

At timepoints coinciding with blood sample collection, including PK, ECGs should be taken prior to blood collection, and, when applicable, before vital signs measurements (example in Figure 2). If a patient experiences Torsade de Pointes, additional concomitant PK samples (i.e., unscheduled) should be collected.

The ECGs will be submitted for a central review. Submission instructions for the central review will be provided in a separate manual. Assessments will include determination of heart rate and rhythm and the PR, QRS, QT, QTcF, and QTcB intervals. Eligibility and clinical decisions may be made based on the local ECG assessment.

[figure not shown]
 Table 3
 Schedule for Triplicate ECG Collection

Cycle	Day	ECG timepoint (window)
Screening	-	Any time within 28 days prior to C1D1
C1	D1	Predose (preferably within 2 h prior to start of infusion) EOI (within 10 min prior to EOI) Postdose* 4 h (± 15 min)
	D8	Postdose* 168 h (± 48 h; but within 30 min prior to PK sample)
	D15	Postdose* 336 h (± 48 h; but within 30 min prior to PK sample)
C2	D1	Predose (within 30 min prior to PK sample) EOI (within 10 min prior to EOI) Postdose* 4 h (± 15 min)
	D8	Postdose* 168 h (± 48 h; but within 30 min prior to PK sample)
	D15	Postdose* 336 h (± 48 h; but within 30 min prior to PK sample)
C3 and C4	D1	Predose (within 30 min prior to PK sample) EOI (within 10 min prior to EOI)
C5, C7 every other cycle	D1	Predose (within 30 min prior to PK sample)
EOT		Any time (but within 30 min prior to PK sample)
Unscheduled		Any time

Abbreviations: C1D1, Cycle 1, Day 1; ECG, electrocardiogram; EOI, end of infusion; EOT, end of treatment; PK, pharmacokinetics.

^{*} Postdose timepoint is counted from start of infusion.

Figure 2 Preferred Sequence for Triplicate Electrocardiogram (ECG), Vital Signs, and Pharmacokinetic (PK) Sample Assessments at End of Infusion (EOI)

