4.8 Safety Analyses

The summary of safety results will be presented.

General common rules

All safety analyses will be performed on the all-treated population, unless otherwise specified, using the following common rules:

- The baseline value is defined as the last non-missing value or measurement taken up to the first dose in the study.
- The analyses of the safety variables will be essentially descriptive and no systematic testing is planned.
- If relevant, selected safety analyses will be summarized by age, sex, racial subgroups, and any pertinent subgroups.
- The toxicity grade according to the Common Terminology Criteria for Adverse Events (CTCAE) version 4.0 will be taken into account in the summary. For patients with multiple occurrences of the same event, the maximum grade is used. If a patient has both missing and non-missing severity grades for treatment-emergent adverse events (TEAEs) within the same preferred term (PT), the patient will be counted under the non-missing severity grade.

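### The absolute QTc categories in SAP 4.8.3 ignore the baseline category, so in this single-arm trial the >450 to 480 ms row mixes entry status with on-treatment change

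*SAP*

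**What the plan says.** SAP 4.8.3 sets out one frequency table: "The following abnormal QTc (including QTcF and QTcB) will be reported by a frequency table". Its first block, headed "At any post-baseline with absolute value", has rows for >450 to 480, >480 to 500 and >500 ms. Its second block, headed "Change from Baseline", has rows for >30 to 60 and >60 ms. The section also plans raw values and changes at each scheduled assessment and a full listing. It plans no shift table, although SAP 4.8.2 plans shifts from baseline for laboratory results.

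Exclusion 21 (Protocol 5.2) reads "Congenital long QT syndrome, or a corrected QTc interval of" 480 ms or more at screening, unless due to a pacemaker or bundle branch block. It does not name the correction formula, whereas the SAP tabulates both QTcF and QTcB.

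Baseline comes from SAP 4.8: "The baseline value is defined as the last non-missing value or measurement taken up to the first dose in the study". It can therefore be a later reading than the one used for eligibility.

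On the number of readings, Protocol 7.4.7 says "Three consecutive (also called triplicate) 12-lead ECGs will be performed at defined timepoints throughout the study". SAP 8.1.2 also brings unscheduled ECGs into the worst values. The SAP does not say how the three tracings at a timepoint are combined. Where a single value is needed, SAP 8.1.3 takes the last measurement of the day.

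**The concern.** The first abnormal band lies almost wholly inside the range in which patients may enter. A patient at 465 ms before the first dose and 465 ms throughout is counted exactly like one who rises from 420 to 465 ms. Exempted patients can start in a higher band. So can a patient whose pre-dose value exceeds the screening value.

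In a randomised trial the control arm would show how many such counts arise without the drug. Here the only internal reference for an absolute category is the patient's own baseline category, and the table leaves it out. Change from baseline in ECGs is a stated secondary safety endpoint (Protocol section 3, Table 2), so a category table tied to baseline would serve the protocol's own aim. What is at stake is how one descriptive safety table is read. No efficacy conclusion depends on it.

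**Working it through.** **Inputs from the documents.** The bands, the entry limit and the baseline rule are as given above. Protocol Table 3 gives these scheduled post-baseline timepoints: Cycle 1 has 4, Cycle 2 has 5, and Cycles 3 and 4 have 2 each, so 4 + 5 + 2 + 2 = 13 by Cycle 4 Day 1. Cycle 5 and end of treatment bring this to 15. The documents state no QTc figure to reproduce, and no QTc mean or SD.

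**Assumptions.** There is no drug effect. A patient's true QTc is T ~ N(mean, SD_between). Each reading is T plus independent N(0, SD_within). A patient enters if the baseline reading is below 480 ms. Mean 405-435 ms, SD_between 16-20 ms, SD_within 7-10 ms, and K = 8 or 12 post-baseline values (fewer than Table 3 schedules through Cycle 4).

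**One patient.** P(any of K values >450) = 1 - Φ((450 - T)/SD_within)^K.
- T = 450, K = 12: 1 - 0.5^12 = 0.9998.
- T = 440, SD_within = 10, K = 12: 1 - Φ(1)^12 = 1 - 0.841^12 = 0.87, against 1 - 0.841 = 0.16 for a single reading.

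A patient who enters in the lowest band is thus almost certain to be counted. One who enters 10 ms below it is likely to be counted through repeated measurement alone.

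**Whole population.** Simulated with no drug effect; figures are approximate.

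| Assumed mean (ms) | Any value >450 | Of those, >450 at baseline | Any value >480 | Worst band above baseline band |
|---|---|---|---|---|
| 405 | 1.7-8.4% | 14-33% | 0.2% or less | 1.3-6.6% |
| 415-425 | 6.5-33% | 20-48% | 0.04-2.6% | 4.6-24% |
| 435 | 38-53% | 38-56% | 1.3-6.7% | 20-36% |

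Values above 500 ms occur in at most 0.3% of patients in any of these settings.

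**What conditioning on baseline removes.** With SD_between 20, SD_within 7 and K = 8, comparing worst band with baseline band lowers the count from about 11.1% to 6.9% (mean 415), 22.7% to 12.8% (mean 425) and 39.2% to 20.3% (mean 435).

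With all 15 timepoints, mean 425, SD_between 20 and SD_within 10, 35.1% have a value >450 ms and 34.4% of those were above it at baseline. Then 35.1 x 0.344 = 12.1 points are carry-over, and 35.1 - 12.1 = 23.0% are newly above 450 ms. Carry-over is removed; noise from taking the worst of many readings stays.

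**Change rows.** With 15 timepoints and no effect, >30 to 60 ms occurs in 0.3% or 13.4% of patients for SD_within 6 or 10 ms, and >60 ms in about 0.0% for both. These rows carry no baseline overlap, but the >30 ms row is still exposed to repeated-measurement noise.

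**Wider ranges.** With 15 timepoints, mean 405-435, SD_between 15-20 and SD_within 6-15 ms, 1.2% to 73.6% have a value >450 ms, and 9-55% of those were above it at baseline. The >480 to 500 ms row holds 0.0-14.2% and the >500 ms row 0.0-2.3%. The high ends need both a high mean and a within-patient SD of 15 ms.

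**The case against.** The case for leaving the table alone is that on-treatment change is already covered. The same table has rows measured against each patient's own baseline, by-visit changes are summarised, and every ECG is listed, so a baseline band can be recovered. Protocol 9.9 plans a separate analysis of drug concentrations against QTc. SAP 4.8 calls the safety analyses essentially descriptive, and no decision rule uses the >450 ms count. Nor does SAP 4.8.3 say that the absolute rows show a drug effect.

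All of this stands, and it keeps the point small. It does not supply the missing summary: neither the change rows nor the by-visit means show which patients in an absolute row were there before dosing.

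A reader might go further and infer that patients with no drug effect fill the whole table, or that a real signal would be hidden. The documents do not support that. The overlap falls mainly on the lowest row, the >480 and >500 ms rows stay small under most assumed values, and the change analyses remain. Nor can one say that the no-effect rate is material in every case: at a mean of 405 ms it can be under 2%.

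It is also fair to object that a shift table deals with only part of the excess. In most settings carry-over is the smaller part, and worst-of-many noise is the larger.

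**Conclusion.** The point holds for the lowest absolute row. The >450 to 480 ms count will include patients already in that band at baseline, and without a control arm it should not be read as on-treatment prolongation. Under the main assumptions about 2-53% of patients would have a value above 450 ms with no drug effect, and about 14-56% of those would have been there before dosing. The width of these ranges reflects the lack of any QTc mean or SD in the documents. That the overlap exists follows from the entry limit and the counting rule; its size does not. The change rows are sound as they are with respect to baseline. This is a minor matter of presentation, worth correcting because the correction is cheap.

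**What to change.** In SAP 4.8.3, add a table for QTcF and one for QTcB that cross-tabulates worst post-baseline band against baseline band (450 or less, >450 to 480, >480 to 500, >500 ms). Report the number of patients whose worst band is higher than their baseline band. Keep the >30 and >60 ms change rows.

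Label the new count as new or worsened versus baseline. It should not be called drug-induced, because noise from taking the worst of many readings remains in it.

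State in the same section how triplicates are combined. Using the mean of the three tracings as the value for the timepoint would reduce that noise.

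The cost is a few sentences in the SAP and one extra table layout, run for each correction, from data already collected. No further ECGs are needed. The downside is a longer output and smaller headline counts, which should be shown beside the unconditional counts so that nothing appears to have been removed.

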4.8.4 Vital Signs

Descriptive statistics (mean, standard deviation, median, and range) for vital signs data, including systolic and diastolic blood pressure, heart rate, respiration rate, and body temperature will be calculated for the raw data and for their changes from baseline at each scheduled assessment.

Summary analyses will include data up to the start of subsequent anticancer therapy/procedure.

All vital signs data will be listed together with body weight.

4.8.5 ECOG Performance Status

Descriptive statistics (mean, standard deviation, median and range) will be calculated for the raw data and for their changes from baseline at each scheduled assessment.

Summary analyses will include data up to the start of subsequent anticancer therapy/procedure.

ECOG performance score data will be listed.

4.8.6 Physical Examinations and Body Weight

Physical examination will be performed according to protocol. Clinically significant findings from the physical examinations will be recorded as medical history (prior to first administration of camidanlumab tesirine) or AEs (subsequent to first administration of camidanlumab tesirine).

Body weight will be listed together with vital signs.

4.9 Efficacy Analyses

Disease assessment will be performed according to protocol. The endpoints described in this section, if not mentioned specifically, use the independent reviewer's evaluation according to the 2014 Lugano Classification criteria before the start of subsequent anticancer therapy or procedure.

Tumor assessment data (target lesions, non-target lesions, new lesions, overall response, SUV max, Deauville score, etc.) will be listed. A separate listing will contain derived data for duration of response (DOR), relapse-free survival (RFS), progression-free survival (PFS), and Overall survival (OS).

4.9.1 Overall Response Rate

Overall response rate is defined as the proportion of patients who achieve either CR or PR as best overall response (BOR) as determined by central review according to the 2014 Lugano Classification criteria before the start of subsequent anticancer therapy or procedure. For the primary ORR analysis in the all-treated population, patients with a CR or PR will be counted as successes and all other patients (including those with missing response information) will be counted as failures.

The order of overall response category is: CR, PR, SD, NE, PD (including disease recurrence/ relapse). The overall response category will be derived based on response assessment performed on or before the start of subsequent anticancer therapy/procedure. Patients without documented subsequent anticancer therapy and/or with missing start date of anticancer therapy will be considered as not having received subsequent anticancer therapy. A BOR of SD can only be made after the patient is on-study for a minimum of 35 days after the first dose of study drug. Any tumor assessment indicating SD before this time period will be considered as NE for BOR if no assessment after this time period is available.

The overall response rate and the corresponding 95% two-sided exact CI will be presented. Subgroup analysis may be provided for disease subtype, disease stage, age group, sex, country, response to the first line and/or most recent line of prior systematic therapy (relapse: CR+PR vs. refractory: SD+PD vs. other: NE + missing), and other relevant variables.

Percent change from baseline in the sum of product of the perpendicular diameters (SPD) for target lesions will be presented for available data in the all-treated population. These data will also be displayed as a waterfall plot, with vertical bars representing the sorted values of best percent reduction for each patient.

A sensitivity analysis of ORR determined by the independent reviewer's evaluation will be conducted for the per-protocol population if relevant.

A sensitivity analysis of ORR will be conducted in which best overall response is determined by investigators.

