9.7.1 Overall Response Rate

The ORR will be defined as the proportion of patients with a best overall response (BOR) of CR or PR. The overall response category will be derived based on response assessment performed on or before the start of subsequent anti-cancer therapy. For the primary ORR analysis in the all-treated population, patients with a CR or PR will be counted as successes and all other patients (including those with missing response information) will be counted as failures.

The percentage of ORR with its 95% confidence interval (CI) will be presented. In contrast to CR, PR, or PD, a BOR of SD can only be made after the patient is on-study for a minimum of 35 days after the first dose of study drug. Any tumor assessment indicating SD before this time period will be considered as a non-evaluable for BOR if no assessment after this time period is available.

9.7.2 **Duration of Response**

The DOR will be defined among responders (CR or PR) as the time from the earliest date of first response until the first date of either disease progression or death due to any cause. The date of disease progression will be defined as the earliest date of disease progression based on central review. For patients who have not progressed or died at the time of the analysis, censoring will be performed using the date of the last valid disease assessment prior to

initiation of a new anticancer therapy (including HSCT). A sensitivity analysis of DOR is planned to be conducted in which the DOR for patients undergoing SCT is not censored at the last evaluable disease assessment prior to SCT. The data will be analyzed by the Kaplan-Meier method. The median DOR and 95% CI will be presented. DOR will be analyzed by response subgroup (CR, PR). Further details will be outlined in the SAP.

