4.9.2 Duration of Response

Duration of response will be defined for patients with CR or PR only as the interval between the date of initial documentation of a response and the date of the first documented evidence of progressive disease based on independent radiographic assessment or death, whichever occurs first. Clinical progression at EOT/EOS without radiographic assessment could be considered as an event in a sensitivity analysis. Patients who have the event after the start of subsequent anticancer therapy/procedure, or are progression-free and alive at the time of

clinical cut-off, or have unknown status, will be censored at the last valid tumor assessment on or before the start of subsequent anticancer therapy/procedure or clinical cut-off time.

Patients with no post-baseline disease assessment will be censored on Day 1.

Duration of response will be estimated and displayed for the all-treated population using Kaplan-Meier methods (SAS® PROC LIFETEST). A Kaplan-Meier plot will be presented.

A sensitivity analysis of DOR will be conducted in which the DOR for patients undergo SCT will not be censored at SCT.

A sensitivity analysis of DOR per investigator assessments will also be conducted.

Subgroup analysis may be provided for disease subtype, disease stage, age group, sex, response to the first line and/or most recent line of prior systematic therapy (relapse: CR+PR vs. refractory: SD+PD vs. other: NE + missing), best response to camidanlumab tesirine (CR/PR), and other relevant variables.

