4.9.6 Progression-free Survival

Progression-free survival is defined as the interval between the date of the first dose and the date of the first disease progression based on independent radiographic assessment or death, whichever occurs first. Clinical progression at EOT/EOS without radiographic assessment could be considered as an event in a sensitivity analysis. Patients who have the event after the start of subsequent anticancer therapy/procedure, or who are progression-free and alive at the time of clinical cut-off, or have unknown status, will be censored at the time of their last valid disease assessment on or before the start of subsequent anticancer therapy/procedure or clinical cut-off.

Patients with no post-baseline disease assessment will be censored on Day 1.

PFS will be estimated and displayed for the all-treated population using Kaplan-Meier methods (SAS® PROC LIFETEST). A Kaplan-Meier plot will be presented.

A sensitivity analysis of PFS will be conducted in which the PFS for patients undergo SCT will not be censored at SCT.

A sensitivity analysis of PFS per investigator assessments will also be conducted.

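### The SAP's response order puts not evaluable (NE) ahead of progressive disease (PD), so a patient whose only assessments are NE and PD is classified as best overall response NE

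*SAP*

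**What the plan says.** SAP 4.9.1 defines ORR as the proportion of treated patients with CR or PR as BOR on central review. It then gives the ranking: "The order of overall response category is: CR, PR, SD, NE, PD (including disease recurrence/ relapse". The same section sets which assessments count: "The overall response category will be derived based on response assessment performed on or before the start of subsequent anticancer therapy/procedure". It also has a minimum-time rule for SD: "Any tumor assessment indicating SD before this time period will be considered as NE for BOR if no assessment after this time period is available". For the primary analysis, "all other patients (including those with missing response information) will be counted as failures".

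Protocol 9.7.1 gives no ranking. It says only: "In contrast to CR, PR, or PD, a BOR of SD can only be made after the patient is on-study", so PD can stand as BOR at any time.

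The time-to-event endpoints find progression by a separate route. PFS (SAP 4.9.6) runs to "the date of the first disease progression based on independent radiographic assessment or death, whichever occurs first". DOR (SAP 4.9.2) runs to "the date of the first documented evidence of progressive disease based on independent radiographic assessment or death, whichever occurs first". RFS (SAP 4.9.5) likewise uses the date of first relapse on independent review, or death.

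**The concern.** NE means that an assessment gave no usable information. PD is an observed treatment failure. Ranking NE as the better outcome turns a known failure into an apparently unassessed patient whenever the two occur together and nothing better was recorded.

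The SAP takes the opposite view elsewhere. In the subgroup definitions of 4.9.1 and 4.9.2, response to prior therapy is grouped with SD and PD as refractory, and NE with missing. No reason is given for treating NE differently in the BOR order. The 35-day SD rule can only affect categories among non-responders, so the SAP clearly intends to derive those categories and not just responder status.

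At stake is the description of why patients did not respond. The error runs in one direction only, from PD to NE. The trial is single-arm, so there is no control group in which the same misclassification would show.

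**Working it through.** **1. The plan's own figures.** The inputs come from SAP 3.1 and Protocol 9.1 and 9.4: N = 100, null ORR 35%, alternative 55%, one-sided alpha 0.025, exact binomial test.

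- The critical value is the smallest r with P(X ≥ r | 100, 0.35) ≤ 0.025, which is r = 45.
- Attained alpha is P(X ≥ 45 | 100, 0.35) = 0.0246.
- Power is P(X ≥ 45 | 100, 0.55) = 0.9824, which agrees with the stated value above 98%.
- The exact lower 95% bounds in Protocol Table 7 also reproduce: 45/100 gives 35.03%, 46/102 gives 35.22%, 47/105 gives 35.05%, 49/108 gives 35.76% and 49/110 gives 35.07%.

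**2. BOR under each order.** BOR is taken as the highest-ranked category among a patient's eligible assessments. SD in the table means SD that meets the 35-day rule.

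| Assessments | SAP order (CR, PR, SD, NE, PD) | PD ahead of NE | Responder? | PFS event? |
|---|---|---|---|---|
| NE, PD | NE | PD | no | yes |
| NE, NE, PD | NE | PD | no | yes |
| PD | PD | PD | no | yes |
| NE | NE | NE | no | no |
| SD, PD | SD | SD | no | yes |
| SD, NE, PD | SD | SD | no | yes |
| PR, NE, PD | PR | PR | yes | yes |

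Only the first two rows change. The last two columns are the same under either order, so every figure in step 1 stands.

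**3. How the pattern can arise.**

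- *NE then PD.* The Week 6 scan is unreadable and Week 12 shows PD. Protocol 7.3 has imaging continue until progression, so this is the main route.
- *PD then NE.* Study drug stops on the Investigator's assessment of progression (Protocol 5.5.1), while BOR uses central review. If central review calls PD and the Investigator does not, scans may go on. SAP 4.9.1 cuts BOR off at subsequent therapy, not at first PD, so a later NE would count. This should be uncommon.
- *Early SD then PD, both before day 35, with nothing later.* The SD becomes NE and then outranks the PD. This is rare.

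**4. Size.** Let m be the number per 100 treated patients with PD and no CR, PR or SD, and q the fraction of those who also have an eligible NE assessment. The shift in percentage points is m × q. Neither quantity is in the documents, so both are assumptions.

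| m per 100 | q = 2% | q = 5% | q = 10% | q = 20% |
|---|---|---|---|---|
| 5 | 0.1 | 0.25 | 0.5 | 1.0 |
| 10 | 0.2 | 0.5 | 1.0 | 2.0 |
| 15 | 0.3 | 0.75 | 1.5 | 3.0 |
| 20 | 0.4 | 1.0 | 2.0 | 4.0 |

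The BOR = PD row is low by this amount and the NE row is high by the same amount. At the upper corner, 20 PD patients would be reported as 16.

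**The case against.** The strongest reply is that nothing inferential depends on this. NE and PD are both failures in the primary analysis. Progression reaches the results through PFS, DOR and RFS, which use the first independently reviewed PD date and never consult BOR. A patient with NE then PD is still a PFS event on the PD date, provided that PD precedes subsequent therapy. SAP 4.9 also lists response at each assessment, so the progression stays visible. All of this stands.

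A reader might infer more than the documents support, in four ways:

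- *That one unreadable scan is enough to turn any progressor into NE.* It is not. A patient who also has CR, PR or qualifying SD keeps that category.
- *That the trial's progression rate is understated.* No such endpoint is defined. Only the BOR = PD and NE rows are affected.
- *That a comparison of central and investigator PD rates would be distorted.* None is planned. The investigator sensitivity analysis in SAP 4.9.1 is of ORR, which does not distinguish NE from PD.
- *That several patients per 100 will certainly move.* The documents cannot show this. In Phase 1 at 45 µg/kg (Protocol 1.3), 18 + 14 = 32 of 37 evaluable patients responded, leaving 5/37, about 14%, as non-responders of every kind, SD included. Those data are investigator-assessed in evaluable patients and do not fix m here. They do show that 20 per 100 should be treated as the top of a range and not as a base case.

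The SAP also does not say in words that BOR is selected by the listed order, and it does not explicitly promise a BOR frequency table. Both are natural readings of 4.9.1, but they are readings.

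None of this removes the defect. Neither document contains a rule that overrides the order, and a programmer following it would return NE for a patient with NE and PD.

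**Conclusion.** The point holds as a minor error in the BOR rule. If the order in SAP 4.9.1 is the selection rule, documented progression is classified as not evaluable for patients who have both NE and PD before subsequent therapy and no CR, PR or qualifying SD. Under the assumed ranges (m from 5 to 20 per 100, q from 2% to 20%) the shift is about 0.1 to 4 percentage points, always from PD to NE. ORR, CRR, DOR, RFS and PFS are unaffected, as are the 45-of-100 threshold, the attained alpha of 0.0246 and the power of 98.2%. It is worth correcting because the rule is wrong as written and errs in one direction.

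**What to change.** In SAP 4.9.1, change the order to CR, PR, SD, PD, NE, and state that BOR is the highest-ranked category in that order among eligible assessments. Reserve NE for patients with no evaluable post-baseline assessment, or whose only evaluable assessment is SD before day 35. Apply the same rule to central and investigator BOR. Giving the reasons for NE in any BOR table would also help the reader.

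The cost is one line of SAP text and one line of programming. Sample size, alpha and power do not change. The only downside is that the reported BOR = PD proportion may be slightly higher.
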